5.2 Inclusion Criteria

Eligibility to participate in the NTMT-02B study is limited to participants with an NT-501 implant in one eye and have completed and exited from the NTMT-01/02 extension study or the Month 24 visit of the Phase 3 study (NTMT-03). No persons shall be excluded based on gender, race, or ethnicity. Study eligibility is to be assessed at Visit 1 (Screening). To participate in this study, the potential participant must meet all the following criteria:

General Inclusion Criteria

- 1. Participants from the Phase 3 study must have completed the Month-24 visit
- 2. Participant in the MacTel Phase 1/2 extension study or the Phase 3 study must exit these studies prior to entering the Bilateral Implant safety study (NTMT-02B)
- 3. Participant must be willing and able to follow the study instructions and be willing and able to complete all required study procedures and visits
- 4. Participant must be willing and able to provide a signed Informed Consent, as well as written documentation in accordance with the relevant country and local privacy requirements, e.g., written data protection consent
- 5. Females of childbearing potential must consent to a pregnancy test before entering the study
- 6. A participant's refusal to allow the collection of blood samples for analysis of serum CNTF, serum Ab or Nab to CNTF, Ab to NTC-201.6A cells and Ab to DFHR levelsin one eye will not exclude the participant from study participation

Ocular Inclusion Criteria

- 1. Participant must have a positive diagnosis of MacTel type 2 with evidence of fluorescein leakage typical of MacTel and at least one of the other features that include hyperpigmentation that is outside of a 500-micron radius from the center of the fovea, retinal opacification, crystalline deposits, right-angle vessels, or inner/outer lamellar cavities in the study eye
- 2. Participant must have steady fixation in the foveal or parafoveal area in the study eye and sufficiently clear media for good quality photographs

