9 ADVERSE EVENTS

An AE is any untoward medical occurrence in humans, whether or not it is considered treatment- or procedure-related, which occurs during the conduct of a clinical trial. Any change in clinical status, ophthalmological assessments, etc., that is considered clinically significant by the study investigator and requires intervention is considered an AE. Medical conditions or diseases present before a participant starts study treatment are only considered AEs if they worsen after the participant starts study treatment (temporal association).

A suspected adverse reaction (related AE) is any event for which there is a reasonable possibility that the treatment caused the AE. A reasonable possibility implies that there is evidence that the treatment caused the event.

NTMT-02B_Protocol_v4.0_21JAN2022 | VV-TMF-136134 | 1.0

NTMT-02B – Bilateral NT-501 Implant Phase 2 Study Protocol Version 4.0 (21 January 2022)

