9.1 Documenting Adverse Events

All AEs, either observed by the investigator or their medical collaborators, or reported by the participant spontaneously, or in response to direct questioning, will be reported. Any AE regardless of severity or potential association with the NT-501 implant, CNTF, or the study procedures must be documented in study records by the investigator and appropriately reported.

All AEs will be reported within the participant's records and in the EDC system. All AEs should be entered into the data system as soon as possible after identification by the site personnel. All AEs will be recorded from the time of surgery through completion of the last study visit.

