12 STUDY RISKS

Studies of intravitreal CNTF delivered by ECT at a nominal daily dose of 20 ng/implant/day have been performed in human participants and is being tested in the ongoing Phase 3 trial in participants with MacTel.

Miosis: In the controlled clinical studies of AMD, RP, and MacTel (Phase 1 and Phase 2 studies), 40 of 180 (22.2%) participants reported miosis as an AE. The prevalence of these findings was confirmed by

the DSMC in their review of the data. The DSMC in their review of these data confirmed that the potential benefit outweighed the risk of this event. Miosis was not observed in 59 participants exposed to a lower dose of CNTF¹⁵.

The intracellular mechanisms through which the trophic factor CNTF regulates cholinergic development were examined in sympathetic neuron cultures.²⁷ Treatment with CNTF increased levels of choline acetyltransferase activity significantly, thus confirming the parasympathetic agonist effect of CNTF. Stimulation of the parasympathetic nervous system (PSNS) results in constriction of the pupillary muscles. Constriction of the pupil occurs when the circular muscle, controlled by the PSNS, contracts. This is the most likely mechanism for CNTF causing miosis. At lower doses in the Phase 2 studies of RP, this effect was not observed.

In addition, in the Phase 2 study of MacTel, pupil size was measured routinely throughout the duration of the study in all participants. The majority of eyes that received the implant had a reduction in the size of the pupil of approximately 1 mm. This effect was not seen in sham eyes but was present in over 90% of all treated eyes. The reason that only approximately 20% of the participants complained about the miosis is possibly related to the lack of any clinical symptoms and of noticeable effect for the participants. Certainly, no participant asked to have the implant removed as a result of noting this well-described drug effect.

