3.4. Baseline Definitions

For all analyses, baseline will be defined as the most recent measurement prior to surgical implantation of the NT-501 device in the study eye. Prior to enrollment into the NTMT-02B study, all subjects previously received an implant as part of their participation in either the Phase 1/2 extension study (NTMT-01/02E) or the Phase 3 study (NTMT-03). As a result, participants' fellow eyes in the prior studies will be the study eye in the current study.

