4.3. Evaluation of Primary Safety Endpoints

All analyses will be conducted using the safety population.

All AEs will be coded using the MedDRA coding system and displayed in tables and data listings using system organ class (SOC) and preferred term.

Analyses of adverse events will be performed for those events that are considered treatment-emergent, where treatment-emergent is defined as any adverse event with onset after the day of surgical implantation through the end of the study (Month 6 ± 14 days post surgery), or any event that was present at baseline but worsened in intensity or was subsequently considered study-related by the Investigator through the end of the study.

Adverse events are summarized by subject incidence rates. In these tabulations, each subject will contribute only once (i.e., the most related occurrence or the most intense occurrence) to each of the incidence rates in the descriptive analysis, regardless of the number of episodes.

The number and percent of subjects will be tabulated overall, by SOC and preferred term within SOC for the following endpoints.

- Treatment-emergent adverse event (TEAE)
- Treatment-related TEAE
- Ocular TEAE occurring in the study eye
- Ocular TEAE occurring in the fellow eye
- Treatment-related Ocular TEAE
- TEAE by maximum grade
- Serious Adverse Events
- TEAEs leading to discontinuation

No formal hypothesis-testing analysis of adverse event incidence rates will be performed.

By-subject listings also will be provided for the following: subject deaths, serious adverse events, and adverse events leading to withdrawal.

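### SAP 4.3 lets an unchanged baseline event become treatment-emergent through relatedness alone, out of line with Protocol 9, so a first-implant effect that a site records as a related AE would be counted

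*SAP*

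**What the plan says.** SAP 4.3 defines a treatment-emergent event by onset after the day of implantation, and then adds "any event that was present at baseline but worsened in intensity or was subsequently considered study-related by the Investigator". Either condition is enough, and the second requires no change in the event.

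Protocol 9 is narrower: "Medical conditions or diseases present before a participant starts study treatment are only considered AEs if they worsen after the participant starts study treatment". Protocol 9.1 sets the collection period: "All AEs will be recorded from the time of surgery through completion of the last study visit". The protocol uses the term TEAE in the synopsis and in 11.3.1 but does not define it. SAP 5 states that nothing differs from the protocol-defined analyses.

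On prior exposure, Protocol 5.2 says "Eligibility to participate in the NTMT-02B study is limited to participants with an NT-501 implant in one eye". In SAP 3.4, "baseline will be defined as the most recent measurement prior to surgical implantation of the NT-501 device in the study eye". Any lasting effect of the first implant is therefore part of baseline.

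Protocol 9.3 asks the investigator to attribute each related AE to the procedure, the implant or CNTF. It does not separate the first implant from the second.

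SAP 4.3 splits plain ocular TEAEs into study eye and fellow eye. The tables of all TEAEs, treatment-related TEAEs and treatment-related ocular TEAEs are not split by eye.

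**The concern.** In patients never treated before, a relatedness route for baseline events would seldom matter. Here every participant already carries a CNTF-releasing implant. Protocol 12 describes miosis as an effect of CNTF. It suggests that delayed dark adaptation may be one too, while saying that its cause is not well understood.

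The first eye is re-examined at Months 1, 3 and 6, including pupil diameter and an implant assessment, so an old effect is in front of the investigator during AE collection. If it is written up as an AE and attributed to CNTF, SAP 4.3 counts it, although it predates the study surgery and has not changed. Such an event says nothing about adding a second implant.

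The tables concerned report the primary safety endpoints of a single-arm study of about 30 people, and no control arm would reveal the excess. The incidence would then depend partly on how each site handles old first-eye findings.

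**Working it through.** The documents give no figure for this point, so there is nothing to reproduce. The check is a comparison of texts followed by an illustration of size.

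**Comparison for an event present before surgery**

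| State after surgery | Protocol 9 | SAP 4.3 |
|---|---|---|
| Worsened | AE | Treatment-emergent |
| Unchanged, not called related | Not an AE | Not treatment-emergent |
| Unchanged, called related | Not an AE | Treatment-emergent |

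The texts part only in the last line.

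**Inputs**
- Minimum of 30 participants (Protocol 4.1, SAP 1.3.1).
- Miosis reported as an AE (Protocol 12): 40/180 = 22.2%, as printed. This pools AMD, RP and MacTel studies.
- Delayed dark adaptation (Protocol 12): 11/55 = 20.0%. The protocol prints 22%; the slip does not affect the point.
- Persistence (Protocol 1.1, Background): implanted eyes had smaller pupils than sham eyes by 0.805 mm at 36 months and 0.844 mm at 48 months, both p < 0.0001. Of the pupil reduction in the Phase 2 MacTel study, Protocol 12 says: "This effect was not seen in sham eyes but was present in over 90% of all treated eyes". These are measurements, not reported AEs, so persistence of miosis as an AE is still an assumption.

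**How many could enter with the effect** (N × p)
- Miosis: 30 × 0.222 = 6.7. Chance of at least one: 1 − (1 − 0.222)^30, above 0.999.
- Delayed dark adaptation: 30 × 0.200 = 6.0, or 30 × 0.22 = 6.6 with the printed rate. Chance of at least one: above 0.99 either way.

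**Fellow-eye row, miosis.** I take the fellow eye in SAP 4.3 to be the first-implanted eye. Let f be the share of carried-in cases that are recorded as AEs and called related. The addition is p × f:
- f = 0: 0 points
- f = 1: 22.2 points (6.7 of 30)

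**Participant-level row, miosis.** Each participant counts once per row. Suppose the second implant causes miosis at the same rate p, independently of the first eye. The incidence is then 1 − (1 − p)(1 − p × f):

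| f | Incidence | Expected of 30 | Addition |
|---|---|---|---|
| 0 | 22.2% | 6.7 | 0 |
| 0.25 | 26.5% | 8.0 | 4.3 points |
| 0.5 | 30.9% | 9.3 | 8.6 points |
| 1 | 39.5% | 11.9 | 17.3 points |

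If the same people get miosis in both eyes, each is already counted for the study eye. The incidence stays at 22.2% whatever f is.

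**The case against.** The strongest reply is that the protocol's own data rules mostly stop the problem before the SAP clause can act. An unchanged pre-existing condition is not an AE under Protocol 9. AE recording starts at surgery, and earlier findings belong in the medical and ophthalmic history. Relatedness is judged for AEs, not for history items. Protocol 9.3 also frames causality in terms of study treatment, which can be read as the implant placed in this study. An investigator who reads it that way should answer no for an old first-eye effect. All of this stands, and it makes the effect conditional.

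Three further replies stand in part. The protocol has no TEAE definition, so the mismatch is with its AE definition. The split by eye keeps first-eye events out of the study-eye ocular table. Listings show relative study day, so a recorded pre-surgery onset would be visible there. None of these protects the tables that are not split by eye.

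It can also be said that a wide definition is cautious, in the spirit of SAP 3.10. That section deals with partial onset dates, where timing is unknown. It does not support counting an event known to predate surgery and to be unchanged.

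A reader might go further and infer that the primary safety rates will be inflated, or that up to 22 points applies to every table. The documents do not support either. Counting needs a site to enter an event that Protocol 9 would leave out, and the 22-point limit belongs to the fellow-eye row alone.

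**Conclusion.** The inconsistency between SAP 4.3 and the AE definition in Protocol 9 is real and is not declared in SAP 5. Its effect depends on site practice. Where Protocol 9 is applied strictly, the clause adds few or no events and serves little purpose. Where it is not, first-implant effects that have not changed are counted in the primary safety tables.

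For miosis the possible inflation is 0 to about 22 points in the fellow-eye row and 0 to about 17 points at participant level. Both upper limits assume that the earlier 22.2% rate carries over, that the effect persists to entry, and that every carried-in case is recorded and called related. The participant-level limit also assumes the same rate after the second implant and independence between eyes. The documents do not give the share called related or the correlation between eyes.

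The analysis is descriptive and no test result is at risk. The clause still deserves correction, because it helps to define the primary outcome and makes the count depend on how sites record old findings.

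**What to change.** In SAP 4.3, delete the alternative that admits a baseline event because the investigator later considers it study-related. An event present at baseline is then treatment-emergent only if it worsens after study surgery, in line with Protocol 9.

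Add a listing, by eye, of any AE records with onset before study surgery and no worsening. Show relatedness only where it was recorded, because it is not collected for history items.

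When the clause is removed, make sure that events starting on the day of surgery stay in the tables. The primary endpoints run from that day, while the SAP 4.3 wording starts after it, and SAP 3.10 sets some incomplete onset dates to the day of treatment so that they count.

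The cost is a small text change in one SAP section and one listing from data already held. No new data collection is needed.

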4.4. Evaluation of Secondary Safety Endpoints

4.4.1. Serum CNTF Levels

Descriptive statistics will be tabulated for Serum levels of CNTF at Months 1, 3, and 6 post surgery. The number of records, mean, standard deviation, geometric mean, 95% confidence intervals of the mean, median, minimum, maximum, geometric mean, geometric standard deviation of CNTF serum levels will be displayed. The confidence interval of the mean will be based on the t-distribution and the confidence interval for the geometric mean will be based on the log-normal distribution.

Change in CNTF from baseline to 1, 3, and 6 months post-surgery will be calculated. At each of these time points, the number of records, mean change, standard deviation, minimum change, maximum change and the 95% confidence interval for the mean change will be tabulated.

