1.1.1 Pharmacokinetics

CNTF is not detectable in the serum of study participants implanted with a single NT-501 implant.

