2 STUDY OBJECTIVES

The overall objective of this study is to evaluate the safety and tolerability of the NT-501 implant, when implanted in both eyes of participants with MacTel type 2.

Primary objective:

• Assess the incidence and severity of adverse events following bilateral ocular implantation of NT-501. Ocular safety will be assessed using ocular examinations, as well as best corrected visual acuity (BCVA) measurements using the Early Treatment Diabetic Retinopathy Study (ETDRS) visual acuity protocol. Systemic safety will be assessed based on the incidence and severity of systemic adverse events (AE)

Secondary objective:

• Assess serum levels of CNTF, the immunogenicity of NT-501 with quantification of antibodies (Ab) to CNTF, neutralizing antibodies (Nab) to CNTF, and Ab to NTC-201.6A cells, as well as Ab to dihydrofolate reductase (DFHR) in samples collected at the Baseline, Month 1, Month-3 and Month-6 study visits.

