3 STUDY ENDPOINTS

Primary Safety Endpoints

- Number and proportion of adverse events from day of surgery through 6 months post implantation
- Number and proportion of severe adverse events from day of surgery through 6 months post implantation
- Number and proportion of ocular adverse events from day of surgery through 6 months post implantation
- Number and proportion of non-ocular adverse events from day of surgery through 6 months post implantation

Secondary Safety Endpoints

- Number and proportion of participants with a loss in BCVA of 15 or more letters from baseline in the study eye using the Early Treatment Diabetic Retinopathy Study (ETDRS) distance chart
- Number and proportion of participants with at least 1 treatment-emergent serious adverse event (SAE)
- Detectable serum levels of CNTF at Months 1, 3 and 6 post-implantations of NT-501
- Number and proportion of participants with serum Ab or Nab to CNTF, Ab to NTC-201.6A cells and Ab to DFHR at Baseline and Months1, 3 and 6 post-implantation of NT-501

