3.10. Missing, Unused, and Spurious Data

In general, there will be no substitutions made to accommodate missing data points. All data recorded on the case report form will be included in data listings that will accompany the clinical study report.

When tabulating adverse event data, partial dates will be handled as follows. If the day of the month is missing, the onset day will be set to the first day of the month unless it is the same month and year as study treatment. In this case, to conservatively report the event as treatment-emergent, the onset date will be assumed to be the date of treatment. If the onset day and month are both missing, the day and month will be assumed to be January 1, unless the event occurred in the same year as the study treatment. In this case, the event onset will be coded to the day of treatment in order to conservatively report the event as treatment-emergent. A missing onset date will be coded as the day of treatment.

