4.2. Demographics and Baseline Characteristics

Demographics, baseline characteristics, medical history, ophthalmic history, vital signs, hematology, chemistry, and urinalysis will be displayed descriptively and through listings. Demographic characteristics (age, sex, body mass index [BMI], and race), and baseline characteristics (Number of correct letters on BVCA by both eyes, spectral domain coherence tomography by both eyes, and baseline CNTF serum level).

Number of subjects, mean, SD, median, minimum, and maximum will be presented for continuous measures; number and percentage of subjects will be presented for categorical measures. The Safety population will be used. No formal statistical comparisons will be performed.

Subjects who report multiple races will be counted for each race reported.

Medical history will include the overall incidence of any finding. Details will be provided in a listing.

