4.4.2. BCVA

The number and percent of subjects with a loss in BCVA of 15 or more letters from baseline in the study eye at any follow-up study visit and by each study visit and the associated 95%

confidence intervals will be tabulated. Confidence intervals will be based on the Clopper-Pearson method.

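### Detectable serum CNTF is a secondary endpoint, but SAP 4.4.1 gives no detection count or below-limit rule; SAP 4.4.3 also drops the protocol's antibody persistence summary without declaring it

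*SAP*

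**What the plan says.** **Endpoint.** Protocol section 3, repeated in SAP 1.3.7, lists among the secondary safety endpoints "Detectable serum levels of CNTF at Months 1, 3 and 6 post-implantations of NT-501". The secondary objective in protocol section 2 is worded in terms of levels: "Assess serum levels of CNTF, the immunogenicity of NT-501". Protocol 11.3.1 likewise refers to systemic levels.

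**Planned CNTF analysis.** SAP 4.4.1: "Descriptive statistics will be tabulated for Serum levels of CNTF at Months 1, 3, and 6 post surgery". The statistics are the number of records, mean, SD, median, minimum, maximum, geometric mean and geometric SD. There is a t-based interval for the mean, a log-normal interval for the geometric mean, and the mean change from baseline with its interval. SAP 4.2 adds a summary of baseline characteristics that includes CNTF ("and baseline CNTF serum level").

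**Other yes/no secondary endpoints.** SAP 4.4.2 counts participants with a BCVA loss of 15 or more letters "in the study eye at any follow-up study visit and by each study visit", and SAP 4.4.3 counts antibody-positive participants, both with Clopper-Pearson intervals. SAP 4.3 covers serious adverse events: "The number and percent of subjects will be tabulated overall, by SOC and preferred term within SOC for the following endpoints".

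**Expected values.** Protocol 1.1.1: "CNTF is not detectable in the serum of study participants implanted with a single NT-501 implant".

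**Data handling.** SAP 3.10: "In general, there will be no substitutions made to accommodate missing data points". The rest of that section deals with partial adverse event dates. Protocol 6.5 says only that the laboratory enters the results.

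**Antibody persistence.** Protocol 11.3.1 plans the number of participants and the titre for three antibodies (to CNTF, neutralizing to CNTF, and to NTC-201.6A) found at Month 3 and still present at Month 6. SAP 4.4.3 has positivity and titres by visit, and fold-rise from baseline. SAP 5 states that nothing has changed from the protocol.

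**The concern.** Three linked gaps arise.

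1. A yes/no endpoint is analysed only as a continuous variable. Followed as written, the CNTF table does not say how many participants had detectable CNTF after the second implant. The other yes/no secondary endpoints all get a count.
2. The continuous summaries need a number for every sample. Every participant has one implant at baseline, so on the protocol's own statement baseline values should be mostly or wholly below the assay limit, and many later values may be too. The supplied SAP text does not say how such results are coded. A geometric mean does not exist if any value is zero. The arithmetic mean, the mean change and the baseline summary move with the coding. Geometric mean titres and the geometric mean fold-rise (GMFR) have the same weakness if antibody-negative samples carry no numeric titre.
3. The Month 3 to Month 6 persistence summary has disappeared, and SAP 5 says nothing has.

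What is at stake is whether the study can state plainly if bilateral implantation produces measurable systemic CNTF, and whether any antibody response lasts.

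**Working it through.** The plan gives no figure to reproduce: there is no sample size calculation and no assay limit. The minimum of 30 participants (protocol 5.1) serves as the illustrative n. Everything marked as assumed below is not in the documents.

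**1. What a detection count would give.** The method is Clopper-Pearson 95%, as already used in SAP 4.4.2 and 4.4.3. With x = 0 the upper limit is 1 − 0.025^(1/n).

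- 0/30: 1 − 0.025^(1/30) = 11.6%, so 0% (0 to 11.6%).
- Protocol 5.2 lets participants refuse these blood samples. If 5 or 10 of 30 refuse (assumed), 0/25 gives 0 to 13.7% and 0/20 gives 0 to 16.8%.
- 3/30: 10.0% (2.1 to 26.5%).

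**2. How the planned summaries depend on coding.** Assumed: the limit is 1 unit; all 30 baseline values are below it; at a later visit 27 are below it and 3 equal 2. Code each below-limit value as s.

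- Arithmetic mean = (27s + 6)/30
- Mean change = 3(2 − s)/30, with t-based interval
- Geometric mean = exp[(27 ln s + 3 ln 2)/30], with log-normal interval

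| Coding s | Arithmetic mean | Mean change (95% CI) | Geometric mean (95% CI) | Detectable |
|---|---|---|---|---|
| 0 | 0.20 | 0.20 (−0.03 to 0.43) | undefined | 10.0% |
| 0.5 (half the limit) | 0.65 | 0.15 (−0.02 to 0.32) | 0.57 (0.49 to 0.67) | 10.0% |
| 1 (the limit) | 1.10 | 0.10 (−0.01 to 0.21) | 1.07 (0.99 to 1.16) | 10.0% |

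The same samples give an arithmetic mean that differs by a factor of 5.5 (1.10/0.20) and a mean change that differs by a factor of 2 in the opposite direction. Once a cut-off is fixed, the percent detectable does not move.

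**3. Fold-rise in antibody titre.** Assumed: 6 of 30 go from negative to a titre of 80, 24 stay negative, and negatives are coded s. Then GMFR = (80/s)^(6/30).

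- s = 1: 80^0.2 = 2.40 (1.23 to 4.67)
- s = 5: 16^0.2 = 1.74 (1.14 to 2.65)
- s = 10: 8^0.2 = 1.52 (1.11 to 2.08)

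**4. Persistence from by-visit counts.** Assumed: 6/30 positive at Month 3 and 6/30 at Month 6. The number positive at both visits lies between max(0, 6 + 6 − 30) = 0 and min(6, 6) = 6, that is, 0% to 20%. The by-visit tables cannot narrow this range, and fold-rise from baseline does not supply the count either.

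**5. SAP 5 against the texts.** For persistence, protocol 11.3.1 plans a within-participant summary and SAP 4.4.3 has none, so the no-changes statement is inaccurate. For CNTF, protocol 11.3.1 itself asks only for levels. That gap is between the named endpoint and its analysis, and is not a conflict with SAP 5.

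**The case against.** The strongest reply concerns the endpoint itself. The other three secondary endpoints open by asking for a count and proportion of participants; the CNTF bullet does not. The objective and protocol 11.3.1 ask for levels, and SAP 4.4.1 supplies them. Reading the bullet as a count is therefore an inference. That is fair, but detectability is a yes/no property, and no statistic in SAP 4.4.1 reports it under either reading.

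Second, the SAP is not silent on the distribution. It plans the median, minimum, maximum and number of records, SAP 3.2 provides n and percent for categorical variables, and listings would allow a later count. This softens the consequence. However, no detectable category or cut-off is defined, and in the example above the median and minimum simply equal s. The maximum would show at most that some value exceeded a limit that the SAP does not state.

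Third, the assay limit and reporting rules may sit in laboratory documents, and any table shells after SAP section 5 were not available to check. This stands as a caveat: the claim is that the supplied text has no rule. Likewise, the titre and GMFR point holds only if negative samples have no numeric titre, and SAP 4.4.3 states no cut-off for a positive antibody result either.

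Fourth, the sizes rest on assumed inputs, and the expectation of undetectable values rests on one background statement. Both are true. The dependence on coding does not need those particular numbers, only that a large share of values fall below the limit.

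None of this answers the persistence omission.

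**Conclusion.** The concern holds. SAP 4.4.1 does not report detectability, which both documents name as a secondary endpoint. Where values fall below the limit, its geometric mean is undefined or set by an unstated coding, and its arithmetic mean and mean change depend on that coding. In the assumed 3-of-30 case the geometric mean is undefined, 0.57 or 1.07 limit units, while the percent detectable is 10.0% throughout. If nobody had detectable CNTF, 0/30 would bound the rate at 11.6%, a useful statement that the planned table cannot make. The size of the coding effect rests on the protocol's statement about single implants carrying over to baseline and, in part, to later visits.

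The SAP also omits the persistence summary planned in protocol 11.3.1, so SAP 5 is inaccurate on that point. The titre and GMFR part is conditional.

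This should be fixed, but its weight is modest: the analyses are descriptive and secondary, no primary endpoint is affected, and persistence could still be counted later from by-subject data, though without a prespecified definition.

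**What to change.** - **SAP 4.4.1:** add n and percent with detectable CNTF at Months 1, 3 and 6 among participants with a sample, with Clopper-Pearson intervals, and show the number sampled. Baseline and any-visit counts are optional.
- **Cut-off:** define detectable by a stated assay limit, and say whether it is the limit of detection or of quantification.
- **Below-limit values:** before database lock, fix one convention for below-limit CNTF and one for negative titres, labelled as conventions. Keep the planned summaries, but when most values are below the limit, flag each one that depends on the convention: arithmetic mean, mean change, geometric mean, geometric mean titre and GMFR. Apply the same convention to the baseline CNTF summary in SAP 4.2.
- **SAP 4.4.3:** add n, percent and titre for participants positive at both Month 3 and Month 6, for the three antibodies named in protocol 11.3.1 (DFHR antibodies and baseline status optional). Otherwise, declare the omission in SAP 5.

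The cost is SAP wording and a few extra tables from samples already scheduled. No new visits or assays are needed.
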